12.4 Response Criteria for Patients with Solid Tumor and Measurable Disease

12.4.1 Evaluation of Target Lesions

Complete Response (CR):

Disappearance of all target and non-target lesions. Any pathological lymph nodes (whether target or non-target) must have reduction in short axis to <10 mm. If immunocytology is available, no disease must be detected by that methodology. Normalization of urinary catecholamines or other tumor markers if elevated at study enrollment (for patients with neuroblastoma).

Partial Response (PR):

At least a 30% decrease in the sum of the diameters of target lesions, taking as reference the baseline sum diameters

Progressive Disease (PD):

At least a 20% increase in the sum of the diameters of target lesions, taking as reference the smallest sum on study (this includes the baseline sum if that is the smallest on study). In addition to the relative increase of 20%, the sum must also demonstrate an absolute increase of at least 5 mm. (Note: the appearance of one or more new lesions is also considered progressions). Note: in presence of SD or PR in target disease but unequivocal progression in non-target or non-measurable disease, the patient has PD if there is an overall level of substantial worsening in non-target disease such that the overall tumor burden

has increased sufficiently to merit discontinuation of therapy

Stable Disease (SD):

Neither sufficient shrinkage to qualify for PR nor sufficient increase to qualify for PD, taking as reference the smallest sum diameters while on study

12.4.2 Evaluation of Non-Target Lesions

Complete Response (CR):

Disappearance of all non-target lesions and normalization of tumor marker level. All lymph nodes must be non-pathological in size (<10 mm short axis)

Note: If tumor markers are initially above the upper normal limit, they must normalize for a patient to be considered in complete clinical response.

Non-CR/Non-PD:

Persistence of one or more non-target lesion(s) and/or maintenance of tumor marker level above the normal limits

Progressive Disease (PD):

Appearance of one or more new lesions and/or *unequivocal progression* of existing non-target lesions. *Unequivocal progression* should not normally trump target lesion status. It must be representative of overall disease status change, not a single lesion increase.

12.4.3 Overall Response Assessment

Table 1: For Patients with Measurable Disease (i.e., Target Disease)

Target Lesions	Non-Target Lesions	New Lesions	Overall Response	Best Overall Response when Confirmation is Required*
CR	CR	No	CR	≥ 28 days Confirmation
CR	Non-CR/Non-PD	No	PR	≥ 28 days Confirmation
CR	Not evaluated	No	PR	
PR	Non-CR/Non-PD/not evaluated	No	PR	
SD	Non-CR/Non-PD/not evaluated	No	SD	documented at least once ≥ 28 days from baseline
PD	Any	Yes or No	PD	no prior SD, PR or CR
Any	PD**	Yes or No	PD	
Any	Any	Yes	PD	

* See RECIST 1.1 manuscript for further details on what is evidence of a new lesion.
 ** In exceptional circumstances, unequivocal progression in non-target lesions may be accepted as disease progression.

Note: Patients with a global deterioration of health status requiring discontinuation of treatment without objective evidence of disease progression at that time should be reported as “*symptomatic deterioration*.” Every effort should be made to document the objective progression even after discontinuation of treatment.

Table 2: For Patients with Non-Measurable Disease (i.e., Non-Target Disease)

Non-Target Lesions	New Lesions	Overall Response
CR	No	CR
Non-CR/non-PD	No	Non-CR/non-PD*
Not all evaluated	No	not evaluated
Unequivocal PD	Yes or No	PD
Any	Yes	PD

* ‘Non-CR/non-PD’ is preferred over ‘stable disease’ for non-target disease since SD is increasingly used as an endpoint for assessment of efficacy in some trials so to assign this category when no lesions can be measured is not advised

Table 3: Overall Response for Patients with Neuroblastoma and Measurable Disease

CT/MRI	MIBG	Bone Scan	Bone Marrow	Catechol	Overall
PD	Any	Any	Any	Any	PD
Any	PD	Any	Any	Any	PD
Any	Any	PD	Any	Any	PD
Any	Any	Any	PD	Any	PD
SD	CR/PR/SD	Non-PD	Non-PD	Any	SD
PR	CR/PR	Non-PD	Non-PD	Any	PR
CR/PR	PR	Non-PD	Non-PD	Any	PR
CR	CR	Non-PD	Non-PD	Elevated	PR
CR	CR	CR	CR	Normal	CR

12.4.4 Overall Best Response Assessment

Each patient will be classified according to his “best response” for the purposes of analysis of treatment effect. Best response is determined as outlined in [Section 12.9](#) from a sequence of overall response assessments.

12.5 Response Criteria for Neuroblastoma Patients with MIBG Positive Lesions

12.5.1 MIBG Positive Lesions

Patients who have a positive MIBG scan at the start of therapy will be evaluable for MIBG response. The use of ^{123}I for MIBG imaging is recommended for all scans. If the patient has only one MIBG positive lesion and that lesion was radiated, a biopsy must be done at least 28 days after radiation was completed and must show viable neuroblastoma.

12.5.2 The following criteria will be used to report MIBG response by the treating institution:

Complete response: Complete resolution of all MIBG positive lesions

Partial Response: Resolution of at least one MIBG positive lesion, with

persistence of other MIBG positive lesions

Stable disease: No change in MIBG scan in number of positive lesions

Progressive disease: Development of new MIBG positive lesions

[figure not shown]
12.5.3 The response of MIBG lesions will be assessed on central review using the Curie scale¹⁴ as outlined below. Central review responses will be used to assess efficacy for study endpoint. See [Section 8.2](#) for details on transferring images to the Imaging Research Center.

NOTE: This scoring should also be done by the treating institution for end of course response assessments.

The body is divided into 9 anatomic sectors for osteomedullary lesions, with a 10th general sector allocated for any extra-osseous lesion visible on MIBG scan. In each region, the lesions are scored as follows. The **absolute extension score** is graded as:

- 0 = no site per segment,
- 1 = 1 site per segment,
- 2 = more than one site per segment,
- 3 = massive involvement (>50% of the segment).

The **absolute score** is obtained by adding the score of all the segments. See diagram of sectors below:

The **relative score** is calculated by dividing the absolute score at each time point by the corresponding pre-treatment absolute score. The relative score of each patient is calculated at each response assessment compared to baseline and classified as below:

1. **Complete response:** all areas of uptake on MIBG scan completely resolved. If morphological evidence of tumor cells in bone marrow biopsy or aspiration is present at enrollment, no tumor cells can be detected by routine morphology on two subsequent bilateral bone marrow aspirates and biopsies done at least 21 days apart to be considered a **Complete Response**.
2. **Partial response:** Relative score ≤ 0.2 (lesions almost disappeared) to ≤ 0.5 (lesions strongly reduced).
3. **Stable disease:** Relative score > 0.5 (lesions weakly but significantly reduced)

to 1.0 (lesions not reduced).

4. **Progressive disease:** New lesions on MIBG scan.

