4.1 Inclusion Criteria

- 4.1.1 **APEC1621SC:** Patient must have enrolled onto APEC1621SC and must have been given a treatment assignment to MATCH to APEC1621J based on the presence of an actionable mutation as outlined in [Appendix VIII](#).
- 4.1.2 **Age:** Patients must be \geq than 12 months and \leq 21 years of age at the time of study enrollment.
- 4.1.3 **BSA:** Patients must have a body surface area $\geq 0.54 \text{ m}^2$ at the time of study enrollment.
- 4.1.4 **Disease Status:** Patients must have radiographically **measurable** disease (See [Section 12](#)) at the time of study enrollment. Patients with neuroblastoma who do not have measurable disease but have MIBG+ evaluable disease are eligible. Measurable disease in patients with CNS involvement is defined as tumor that is measurable in two perpendicular diameters on MRI and visible on more than one slice.

Note: The following do not qualify as measurable disease:

- malignant fluid collections (e.g., ascites, pleural effusions)
- bone marrow infiltration except that detected by MIBG scan for neuroblastoma
- lesions only detected by nuclear medicine studies (e.g., bone, gallium or PET scans) except as noted for neuroblastoma
- elevated tumor markers in plasma or CSF
- previously radiated lesions that have not demonstrated clear progression post radiation
- leptomeningeal lesions that do not meet the measurement requirements for RECIST 1.1.

4.1.5 **Performance Level:** Karnofsky $\geq 50\%$ for patients > 16 years of age and Lansky ≥ 50 for patients ≤ 16 years of age (See [Appendix I](#)). Note: Neurologic deficits in patients with CNS tumors must have been relatively stable for at least 7 days prior to study enrollment. Patients who are unable to walk because of paralysis, but who are up in a wheelchair, will be considered ambulatory for the purpose of assessing the performance score.

4.1.6 **Prior Therapy**

4.1.6.1 Patients must have fully recovered from the acute toxic effects of all prior anti-cancer therapy and must meet the following minimum duration from prior anti-cancer directed therapy prior to enrollment. If after the required timeframe, the numerical eligibility criteria are met, e.g. blood count criteria, the patient is considered to have recovered adequately.

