- i. XRT/External Beam Irradiation including Protons: ≥ 14 days after local XRT; ≥ 150 days after TBI, craniospinal XRT or if radiation to $\geq 50\%$ of the pelvis; ≥ 42 days if other substantial BM radiation.

Note: Radiation may not be delivered to “measurable disease” tumor site(s) being used to follow response to subprotocol treatment.

- j. Radiopharmaceutical therapy (e.g., radiolabeled antibody, 131I-MIBG): ≥ 42 days after systemically administered radiopharmaceutical therapy.
- k. Patients must not have received prior exposure to BVD-523FB (ulixertinib) or other ERK inhibitors.

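### Section 12.5 has no rule for irradiated MIBG lesions when more than one is present, so in MIBG-only neuroblastoma a radiation effect can be scored as a response to the study drug

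*Combined protocol and SAP*

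**What the plan says.** All references are to the combined protocol and SAP.

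- **Entry.** Section 4.1.4: "Patients with neuroblastoma who do not have measurable disease but have MIBG+ evaluable disease are eligible". The same section lists what does not qualify as measurable disease, including "previously radiated lesions that have not demonstrated clear progression post radiation".
- **Prior radiation.** Section 4.1.6.1.i sets the minimum interval before enrollment at "≥ 14 days after local XRT". A note there bars radiation to measurable-disease "tumor site(s) being used to follow response to subprotocol treatment".
- **Safeguard in the MIBG section.** Section 12.5.1: "If the patient has only one MIBG positive lesion and that lesion was radiated, a biopsy must be done at least 28 days" after the end of radiation, and the biopsy must show viable neuroblastoma. Section 12.5 says nothing on irradiated sites when there are two or more.
- **Local PR rule (12.5.2).** "Resolution of at least one MIBG positive lesion" while others persist.
- **Central rule (12.5.3).** Segment scores of 0 to 3 are summed and divided by the pre-treatment sum. A relative score of 0.5 or less is PR; above 0.5 and up to 1.0 is SD. Central review decides the efficacy endpoint.
- **Overall response (Table 4, 12.5.4).** In MIBG-only disease, an MIBG PR becomes an overall PR if CT/MRI shows no new lesion and bone scan and marrow are not PD.

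**The concern.** The protocol accepts elsewhere that an irradiated lesion needs evidence of active tumor before it is relied on: clear progression in Section 4.1.4, a biopsy in Section 12.5.1. With two or more MIBG lesions no such condition is stated, and neither PR rule leaves out an irradiated site. A site that was irradiated shortly before enrollment, is still avid at baseline and clears later lowers the score whatever the drug does.

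Central review cannot catch this, because the scoring rule itself produces the result. Objective response is the primary endpoint and three responses in 20 make the trial a success. Neuroblastoma is a listed expansion histology (Appendix VII), and three responses in one histology open an expansion cohort (11.3.2).

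**Working it through.** **1. The plan's own figure.** Section 11.3.1 gives N = 20, success at 3 or more responses, 5% versus 25%, alpha 10%, power 90%. The exact binomial gives:
- P(X ≥ 3 | 20, 0.25) = 0.909, which agrees with the stated 90% power.
- P(X ≥ 3 | 20, 0.05) = 0.0755. The 10% is the ceiling of the exact design, and the attained error is 7.5%.

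**2. Local rule.** With any number of lesions from two upward, if the irradiated one resolves and others persist, 12.5.2 gives PR.

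**3. Central rule.** Let I be the baseline score of the irradiated segments, all of which clear, and O the score of the other segments, unchanged. The relative score is R = O / (I + O). R ≤ 0.5 exactly when I ≥ O, that is, when the cleared sites held at least half of the baseline score.

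| I | O | R | Central result |
|---|---|---|---|
| 1 | 1 | 1/2 = 0.50 | PR |
| 1 | 2 | 2/3 = 0.67 | SD |
| 1 | 3 | 3/4 = 0.75 | SD |
| 2 | 2 | 2/4 = 0.50 | PR |
| 2 | 3 | 3/5 = 0.60 | SD |
| 3 | 3 | 3/6 = 0.50 | PR |
| 3 | 4 | 4/7 = 0.57 | SD |

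With three, four or five single-site lesions in separate segments and one cleared, R is 0.67, 0.75 or 0.80: SD each time. With three non-massive lesions in one segment and one cleared, the segment scores 2 before and after, so R = 2/2 = 1.0, also SD.

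**4. Two lesions, both irradiated.** The condition in 12.5.1 is not met, because there is not a sole lesion, so no proof of viable tumor is asked for. If both clear, uptake has fully resolved and the MIBG result is CR (subject to the marrow condition in 12.5.3 if marrow was involved at enrollment). This case does not depend on the 0.5 threshold.

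**5. Effect on the decision rule.** Suppose one of the 20 patients is certain to be a false responder. Success then needs 2 or more responses from the other 19: P(X ≥ 2 | 19, 0.05) = 0.245, against 0.0755 without such a patient.

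The documents give no frequency. Let q, an assumption, be the chance that the cohort holds one such patient. Then P(success | 5%) = 0.0755 + q × (0.2453 − 0.0755):

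| q | P(success at a true 5%) |
|---|---|
| 0 | 7.5% |
| 5% | 8.4% |
| 10% | 9.2% |
| 25% | 11.8% |
| 50% | 16.0% |
| 100% | 24.5% |

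The 10% ceiling is reached at q = (0.10 − 0.0755) / (0.2453 − 0.0755) = 0.0245 / 0.1698, about 14%.

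**The case against.** **Existing wording may already cover this.** The list in 4.1.4 makes exceptions for neuroblastoma in its marrow and nuclear-medicine items but none in its irradiated-lesion item, so that item can be read as reaching MIBG sites. The note in 4.1.6.1.i describes sites by their use in following response. This stands as far as it goes: a reader might infer that no rule on irradiated sites touches MIBG disease, but the text is ambiguous on that. The broad reading still does not close the gap. The 4.1.4 item decides what qualifies a patient; someone who qualifies on a non-irradiated lesion keeps the irradiated one in the Curie numerator and denominator. A ban on radiation to any MIBG site used for response would also sit badly with 12.5.1, which allows for an irradiated sole lesion.

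**12.5.1 may only establish that active disease exists.** On that view, other non-irradiated lesions make a biopsy unnecessary. This is a fair reading of its purpose, which the text does not state. It does not help when all of several lesions were irradiated, and it leaves the scoring question open.

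**The affected group is narrow.** This stands. With measurable disease, Table 3 (12.4.3) gives overall SD when CT/MRI is SD, even if MIBG is PR. PR also needs two determinations (12.9), although a durably cleared site would meet that. The 14 days are the minimum for local radiation only; 4.1.6.1.i requires 42 or 150 days after larger marrow-bearing, pelvic, craniospinal or total body fields.

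**Conclusion.** The gap is real and confined to MIBG-only neuroblastoma with more than one lesion. The local rule then always gives PR when an irradiated lesion clears and others persist. The central rule does so only when the cleared irradiated sites held at least half of the baseline score. Two irradiated lesions that both clear can give an MIBG CR with no proof of viable tumor.

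Two stronger readings are tempting and not supported:
- That any patient with two or more lesions gets PR on both rules. The central rule sets the endpoint and gives SD when one of three or more single-site lesions in separate segments clears.
- That the trial's false-positive rate is 24.5%. That figure assumes a certain false responder. It falls in proportion to the chance of such a patient and stays under 10% if that chance is below about 14%.

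The calculation assumes at most one such patient, a true 5% response rate in the other 19, and no change in the non-irradiated lesions. The correction is worth making because the bias runs one way, three responses decide the trial, and the remedy is cheap.

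**What to change.** - **Scoring.** State in 12.5.1 to 12.5.3 that a site irradiated before enrollment is left out of the baseline and all later Curie scores, and of the local PR rule, unless progression after radiation is documented or a positive post-radiation biopsy is already available. New uptake at that site still counts for progression.
- **Mixed segments.** Score a segment that holds both kinds of site on its non-irradiated sites only.
- **Zero baseline.** A patient whose remaining baseline score is zero cannot be counted as a responder on MIBG.
- **Data.** Record the radiation field on the baseline MIBG form and give it to central review.
- **Reconcile.** Make 4.1.4, 4.1.6.1.i and 12.5.1 agree on whether the radiation wording written for measurable disease applies to MIBG-evaluable sites. Where radiation may be given is for the study team and is not proposed here.

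The cost is wording and one entry on a form, with no added procedure. The downside is that some patients have a smaller baseline score, and a few cannot be responders on MIBG.

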12.2 Progression-Free Survival

Progression-free survival (PFS) is defined as the duration of time from start of subprotocol treatment to time of progression or death, whichever occurs first.

Development of new disease or progression in any established lesions is considered progressive disease, regardless of response in other lesions – e.g., when multiple lesions show opposite responses, the progressive disease takes precedence.

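### Sections 12.5.2 and 12.5.3 count only new lesions as MIBG progression, in conflict with Section 12.2, and leave a Curie relative score above 1.0 without a category

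*Combined protocol and SAP*

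**What the plan says.** - **Section 12.2 (PFS).** PFS runs from the start of treatment to progression or death, and "Development of new disease or progression in any established lesions is considered progressive disease, regardless of response in other lesions".
- **Section 12.5.2 (institutional MIBG rule).** Progression is "Development of new MIBG positive lesions". Stable disease is "No change in MIBG scan in number of positive lesions".
- **Section 12.5.3 (central MIBG rule, Curie scale).** Each of ten sectors is scored 0 to 3. Scores 1 and 2 count sites, while the top score measures extent: "3 = massive involvement (>50% of the segment"). The relative score is obtained by "dividing the absolute score at each time point by the corresponding pre-treatment absolute score". Stable disease runs from above 0.5 "to 1.0 (lesions not reduced"). Progression is "New lesions on MIBG scan". On its role: "Central review responses will be used to assess efficacy for study endpoint". A note asks the treating institution to do the same scoring.
- **Table 4 (Section 12.5.4).** The overall response for MIBG-only disease is read from an MIBG entry of PD, SD, PR or CR together with CT/MRI, bone scan, marrow and catecholamines.
- **Section 11.7.** A progression called by the treating institution is a PFS event even if central review disagrees. PFS by central review is a secondary analysis, reported only if there are enough disagreements.
- **Section 12.9.1.** The reference for progression is the smallest measurement since treatment began.

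**The concern.** The section that defines PFS treats growth of existing disease as progression. The two sections that tell readers how to classify an MIBG scan do not. A scan on which existing sites have plainly extended, with no new site, is handled differently by each section, and 12.5.3 gives it no label at all.

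This matters most for patients admitted on MIBG-evaluable disease without measurable disease (Section 4.1.4). Footnote 4-C to the Section 8.1 table does not require CT/MRI in their follow-up, so MIBG may be the only routine imaging of their existing lesions. At stake is the date of the PFS event in these patients. An unlabeled scan also leaves open whether the Section 5.2 condition of at least stable disease is met.

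**Working it through.** The plan states no PFS sample size, event count, median or precision, so there is no figure to reproduce. The check has five steps.

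**1. One scan under each rule.** Take a scan on which existing sites have progressed, the number of sites is unchanged, and no other component shows progression.

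| Rule | Call |
|---|---|
| 12.2 | PD |
| 12.5.2 | SD (lesion count unchanged) |
| 12.5.3, relative score above 1.0 | None: not CR or PR, above the SD limit, no new lesion |
| Table 4 | SD row if the 12.5.2 call is entered; no row if the 12.5.3 result is entered |

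**2. Can a score above 1.0 occur without a new site?** Relative score = current absolute score / pre-treatment absolute score. Without a new site, a segment can rise only from 1 to 3 or from 2 to 3, because going from 1 to 2 needs a second site.

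- One involved segment: 3/1 = 3.0, or 3/2 = 1.5.
- Three segments, all from 2 to 3: 9/6 = 1.5.
- Five involved segments, one worsening: (5 − 1 + 3)/5 = 1.4 if all began at 1; (10 − 2 + 3)/10 = 1.1 if all began at 2.
- Ten involved segments, one worsening: (10 − 1 + 3)/10 = 1.2, or (20 − 2 + 3)/20 = 1.05.
- Of the 285 distinct non-zero ten-segment baseline patterns, the 10 made up only of 0s and 3s cannot exceed 1.0 in this way. The other 275 can.

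The last count shows that the state is reachable. It does not show how often patients reach it.

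**3. Reference score.** Suppose two segments score 3 at baseline (total 6), shrink to 1 each (total 2), then regrow in the same sites to 3 each (total 6).

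- At best response: 2/6 = 0.33, which is PR.
- After regrowth: 6/6 = 1.0, which is SD under 12.5.3.
- Against the smallest score: 6/2 = 3.0.

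Section 12.9.1 takes the smallest measurement as its reference, whereas 12.5.3 always divides by baseline. Regrowth after response is therefore SD on the MIBG component, however large relative to the smallest score, while the score stays at or below 1.0 and no lesion counts as new.

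**4. Route to PFS.** Under 11.7 the main analysis uses local calls. Section 8.3.1 sends only responders and patients with stable disease of at least 6 cycles to central review. The effect therefore runs mainly through 12.5.2. Every progression trigger in 12.5.2 is also a trigger in 12.2, but not the reverse. For a given patient, the event date under 12.5.2 is the same as under 12.2 or later, never earlier.

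**5. Route to response rate.** A relative score above 1.0 is neither CR nor PR. Section 12.3.1.1 counts evaluable patients without a confirmed response as non-responders, so an unclassified scan adds no response to the rule of at least 3 in 20.

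**The case against.** The strongest case on the other side is that PFS is protected elsewhere in the protocol.

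- The main analysis takes local calls whatever central review says, and central PFS is only a conditional secondary analysis.
- A site that applies 12.2 records the event on time.
- Table 4 gives overall PD for a new CT/MRI lesion, bone-scan progression or marrow progression, and 12.6.1 has a quantitative marrow rule.
- Section 10.1 accepts clinical or serum-marker evidence, and footnote 4 in Section 8.1 lets the investigator leave clinical or laboratory progression unconfirmed by imaging.
- The sentence about the study endpoint most naturally refers to response, which is the primary endpoint.

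All of this stands, and it limits the finding. A reader might infer that the central rule inflates PFS, or that a worsening patient cannot progress until a new lesion appears or the patient dies. The documents support neither. The first overlooks the local-call rule in 11.7, and the second overlooks the other routes just listed.

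These points do not remove the conflict. The local rule in 12.5.2 has the same omission, and the local Curie scoring asked for in 12.5.3 gives no label. For MIBG-only patients the Table 4 CT/MRI route needs a new lesion, and CT/MRI is not required in follow-up.

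**Conclusion.** The contradiction is in the text: 12.2 counts progression of established lesions, while 12.5.2 and 12.5.3 count only new ones. A relative score above 1.0 without a new lesion is reachable and unclassified. In MIBG-evaluable neuroblastoma, PFS events may be recorded late or inconsistently according to the section a site follows, unless another component or clinical or marker evidence shows progression.

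The size cannot be computed. The documents give no number of MIBG-evaluable patients, no event rate, and no frequency of worsening without new lesions. Each such patient would be 1/20 = 5% of the primary cohort. An overstatement of the trial's PFS estimate is therefore not shown, and neither is any effect on the primary response rate. The finding assumes that at least some sites classify MIBG scans by 12.5.2. It is a minor point that is easy to repair.

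**What to change.** Reconcile 12.5.2, 12.5.3 and Table 4 with 12.2, and with the smallest-measurement reference for progression in 12.9.1. The revised text should:

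- give every relative score, including those above 1.0, exactly one category, with a matching row in Table 4;
- state whether the reference for MIBG progression is the baseline score or the smallest score on study;
- say how worsening of existing lesions is treated, in the same terms for the institutional and the central reading;
- write the PR line in 12.5.3 as a single range, since it now gives two upper limits (0.2 and 0.5).

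Progressive disease leads to removal from therapy (Section 10.1), so the study committee should set any cut-off; none is proposed here. The cost is a few lines of text. The possible downside is an occasional earlier progression call caused by variability in scoring.
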